Appendix 3. PROMIS Score Conversion Tables

Appendix 4. Example SAS Code

Example SAS code for MMRM Model

Example SAS code for ANCOVA Model

```
proc mixed data = dataset;
    class treatment therapy cancer;
    model cfb = treatment base therapy cancer / residual outp=resid_out;
    lsmeans treatment / diff cl alpha=0.1;
    ods output lsmeans=lsmeans_out;
    ods output diffs=diffs_out;
run;
```

Example SAS code for Cox Proportional Hazards Model:

Example SAS code for Cumulative Incidence Plots:

```
proc lifetest data = dataset method=km plots=cif outcif=cifatrisk
intervals=0 to 12 by 4;
    strata treatment;
    time day*censor(1) / eventcode=0;
run;
```

NOTE: the censor variable has a value = 1 when the related time is censored and has a value = 0 when the event of interest occurs. There should be no other values available for this censored variable in this dataset (including missing values). If required, missing observations should be removed prior to analysis.

Example SAS code for Proportion of Responses (with multiple imputation):

Assume the SAS dataset is in a long format. The variable 'treatment' should be coded similar to 'Placebo', 'Ponsegromab 100mg', 'Ponsegromab 200mg', 'Ponsegromab 400mg', so that 'Placebo' comes first.

NOTE: If a participant discontinues due to death, they should be included in the imputation, but once their value has been imputed then they should be classified as a non responder.

```
proc sort data=analysis out=analysis long;
   by subjid time treatment therapy cancer base;
run;
* Create wide dataset for multiple imputation;
proc transpose data= analysis long out=analysis wide prefix=wk;
   by subjid treatment therapy cancer base;
   id time;
   var pcfb;
run;
* Perform multiple imputation;
proc mi data=analysis wide seed=169 nimpute=20 out=analysis mi;
   class treatment;
   fcs nbiter=10 reg(/details);
   var base treatment therapy cancer wk4 wk8 wk12;
* Need to add in here code to classify any participants that discontinue
due to death as non responders;
* Determine responders and non-responders at Week 12 for all imputed
  datasets;
data analysis mi 12;
   set analysis mi;
   if wk12 >= 3.5 and wk12 ne . then resp = 1;
   if wk12 < 3.5 and wk12 ne . then resp = 0;
run:
* Create datasets and combine proportions;
proc freq data=analysis mi 12;
   tables imputation * treatment *resp / out=prop mi outpct;
run;
data prop mi 0;
   set prop mi;
   if resp=0;
   keep _imputation_ treatment count;
   rename count=count 0;
run;
```

```
data prop mi 1;
   set prop mi;
   if resp=1;
   keep imputation treatment count;
   rename count=count_1;
run;
data prop mi combined;
  merge prop mi 0 prop mi 1;
  by _imputation_ treatment;
   total = count 0 + count 1;
  p = count 1 / total;
   q = count 0 / total;
   se p = sqrt((p*q)/total);
run;
proc sort data=prop mi combined; by treatment imputation ; run;
proc mianalyze data=prop mi combined alpha=0.1;
  by treatment;
  modeleffects p;
   stderr se p;
   ods output parameterestimates=prop mi out;
```

Example SAS code for Logistic Regression Model (with multiple imputation):

The same imputed datasets as produced above for the 'Proportion of Responses' will be utilized. Note: the imputed dataset should be ordered with 'Resp'=1 first to ensure that the odds ratios are for a response = 1 and the reference group is Placebo.

```
* Fit logistic regressions to each imputed dataset and combine results;
proc sort data=analysis mi 12; by imputation treatment descending resp;
run;
proc genmod data=analysis mi 12 order=internal descending;
   by imputation;
   class resp treatment;
   model resp = treatment therapy cancer base
                / dist=bin link=logit alpha=0.1;
   lsmeans treatment / cl diff alpha=0.1 exp;
   ods output lsmeans=odds mi diffs=oddsrat mi;
run;
*Odds ratios;
data oddsrat mi;
   set oddsrat mi(where=( TREATTXT="Placebo"));
   if TREATTXT = ' Ponsegromab 100mg ' then treatment = 100;
   if TREATTXT = ' Ponsegromab 200mg ' then treatment = 200;
   if TREATTXT = ' Ponsegromab 400mg ' then treatment = 400;
   if treatment = . then delete;
   SE = StdErr;
run;
proc sort data=oddsrat mi; by treatment imputation; run;
```

```
proc mianalyze data=oddsrat mi alpha=0.1;
   by treatment;
   modeleffects estimate;
   stderr SE;
   ods output parameterestimates=OddsRatios mi out;
run;
data OddsRatios mi out;
   set OddsRatios mi out;
   oddsratio = exp(estimate);
   LCLoddsratio = exp(LCLMean);
   UCLoddsratio = exp(UCLMean);
run;
* Odds;
data odds mi;
set odds mi;
   if TREATTXT = 'Placebo' then treatment = 0;
   if TREATTXT = 'Ponsegromab 100mg ' then treatment = 100;
   if TREATTXT = 'Ponsegromab 200mg ' then treatment = 200;
   if TREATTXT = 'Ponsegromab 400mg ' then treatment = 400;
   if treatment = . then delete;
   SE = StdErr;
run:
proc sort data=odds mi; by treatment imputation; run;
proc mianalyze data=odds mi alpha=0.1;
   by treatment;
   modeleffects estimate;
   stderr SE;
   ods output parameterestimates=Odds_mi_out;
run;
data Odds mi out;
   set Odds mi out;
   odds = exp(estimate);
   LCLodds = exp(LCLMean);
   UCLodds = exp(UCLMean);
run;
```

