5.3.1. Multiple Imputation

For summarizing the proportion of responses (e.g. response as defined by a ≥3.5% increase from baseline in body weight at Week 12), all percent change from baseline data from the censored analysis set will be included (all timepoints up to and including Week 12, i.e. Weeks 4, 8 and 12). A multiple imputation method will be implemented, using a multivariate imputation method by chained equations, which is still valid with an arbitrary missing data pattern. The model will include baseline and treatment. Additional terms for type of therapy [i.e. platinum or not] and type of cancer will also be included, as appropriate. Twenty sets of imputations of each missing value will be constructed from the multiple imputation method and the proportion of responses by treatment will be determined with associated standard errors utilizing a normal approximation and will be combined using standard multiple imputation techniques proposed by Rubin² to yield overall estimates and CIs. If there is more missing data in the study than anticipated, the number of imputation sets may be increased as required. Note that data for participants who die during the study will be included in the imputation but will then be classed as having a 'Non-response' after imputation.

For logistic regression, all percent change from baseline data from the censored analysis set will be included (all timepoints up to and including Week 12, i.e. Weeks 4, 8 and 12). The same imputed datasets as produced for the proportion of responses above will be utilized, where a Logistic Regression model (as described in Section 5.2.8) will be applied to each of the 20 imputed datasets separately. Parameter estimates, of the log odds for each treatment and log odds ratios for each dose relative to placebo, will be combined using standard multiple imputation techniques proposed by Rubin² to yield overall estimates of the log odds and log odds ratios and their associated standard errors and will be used to create 90% CIs on the log-odds scale. The log odds (and CIs) and log odds ratios (and CIs) will be back transformed into odds and odds ratios (and CIs) for final reporting.

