6.5. Subset Analyses

Additional analyses will be performed on the primary endpoint (change from baseline body weight) to assess the effect of the following two subgroup factors:

- Type of cancer (i.e. NSCLC, PANC or CRC)
- Type of therapy (ie, platinum or not) at randomization [+/- 28 days]
- Screening Roche GDF-15 (dichotomized using < or ≥ overall study median level (or an alternative cut-point, if appropriate))

These analyses will be performed on the censored analysis set, as defined in Section 4.

For each subgroup factor, absolute values, changes from baseline and percent changes from baseline in body weight will be summarized descriptively by subgroup factor, treatment group and timepoint, as described in Section 5.2.1. Tables will include baseline and all post-baseline timepoints.

For each subgroup factor, change from baseline in body weight will be analyzed using an MMRM model, as described in Section 6.1.1.1. Additional terms for the subgroup factor and its interaction with treatment group, time and the treatment-by-time interaction, will be included in the model. Other terms (eg, type of therapy [i.e. platinum or not] and type of cancer; described in Section 6.1.1.1) will be dropped from the model, as appropriate. LS means (and 90% CIs) and mean differences versus placebo (and 90% CIs) will be provided. The p-values for the subgroup interaction terms will be included in the tables, e.g. as a footnote. No adjustments will be made for multiplicity.

If the MMRM model cannot be fitted to the data, or the model is deemed inappropriate, the model may be simplified, or the analysis may not be performed.

Additionally, screening Roche GDF-15 will be plotted vs Week 12 change from baseline body weight using a scatterplot. The plot will include all participants and may be colored/trellised by different cancer types and/or type of therapy.

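### The example imputation and logistic code for the weight-gain responder analysis leaves cancer type out of CLASS, so it either stops with an error or fits three unordered cancers as one linear score

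*SAP*

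**What the plan says.** SAP 3.4.13 and 6.4.13 define response as a weight gain of at least 3.5% from baseline at Week 12. They report it as percentages after multiple imputation and through a logistic regression. SAP 5.3.1 says of the imputation model: "Additional terms for type of therapy [i.e. platinum or not] and type of cancer will also be included, as appropriate". SAP 5.2.8 says the same two terms may be added to the logistic model where appropriate, and asks for odds, odds ratios, 90% intervals and p-values. SAP 6.5 lists the cancer types as NSCLC, PANC and CRC, and therapy as platinum or not.

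Three code blocks in SAP Appendix 4 use these covariates:

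- **ANCOVA:** the class statement is "class treatment therapy cancer".
- **PROC MI:** the class statement is "class treatment" and nothing more, while the variable list is "var base treatment therapy cancer wk4 wk8 wk12".
- **PROC GENMOD:** the class statement is "class resp treatment", while the model statement begins "model resp = treatment therapy cancer base".

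The appendix says how treatment should be coded, using text labels. It gives no coding for therapy or cancer.

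**The concern.** A single variable holding three nominal categories works as intended only if it is declared in CLASS. Otherwise SAS needs it to be numeric and treats the numbers as measurements. NSCLC, PANC and CRC have no natural order or spacing, so the fitted line would reflect whichever codes the database happens to use. The same imputed datasets feed both the responder percentages and the logistic regression, so a numeric coding would affect the results at two points without any warning in the log. The ANCOVA block treats the same covariates as categorical, which suggests the difference is an oversight.

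**Working it through.** The plan gives no figure on this point, so there is none to reproduce. The check compares the statements, counts parameters, and then illustrates the size.

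**1. What the code does with `cancer`.**
- *Text values:* a model variable outside CLASS must be numeric, so both procedures stop with an error. The failure is visible and no result is produced.
- *Numeric values:* both procedures run and fit one slope.

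**2. Degrees of freedom.** A three-level factor takes 3 − 1 = 2. A slope takes 1. The logistic model then has 1 (intercept) + 3 (treatment) + 1 (therapy) + 1 (baseline) + 1 (cancer) = 7 parameters instead of 8. Each imputation regression also loses one.

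**3. What the slope imposes.** With codes 1, 2, 3 and slope b, the middle type contributes 2b = (b + 3b)/2, exactly midway between the other two. Three types can be ordered in 3! = 6 ways. Reversing an order only changes the sign of b, so 6/2 = 3 distinct fits are possible, one for each choice of middle type.

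**4. Therapy.** Two levels need 1 degree of freedom under either treatment, so the fit is the same. As a check, recoding therapy from 0/1 to 1/2 left the 400 mg log odds ratio at 0.2016 both times. Only the per-arm LS-means odds change, because they are evaluated at the mean of a non-CLASS covariate but with equal weights over CLASS levels.

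**5. Illustrative size.** The final logistic step only was simulated, without imputation. From the protocol: 168 participants, 42 per arm (9.5), and a cancer mix of 4:4:3 for NSCLC, CRC and PANC (4.3). Assumed: treatment log odds of 0, 0.5, 0.8 and 1.2, intercept −1, half of participants on platinum, no therapy or baseline effect, and the cancer effects shown. There were 300 runs per row. Entries are the mean absolute difference between numeric and factor coding in the 400 mg versus placebo log odds ratio, with the largest single run in brackets.

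| Assumed log odds: NSCLC, CRC, PANC | CRC coded in the middle | PANC in the middle | NSCLC in the middle |
|---|---|---|---|
| 0, 0, 0 | 0.026 (0.248) | 0.029 (0.250) | 0.024 (0.288) |
| 0, −1, 0 | 0.099 (0.451) | 0.053 (0.340) | 0.048 (0.296) |
| 0, −1, −0.5 | 0.068 (0.461) | 0.027 (0.172) | 0.078 (0.482) |
| 0, −0.5, −1 | 0.029 (0.211) | 0.063 (0.409) | 0.079 (0.600) |

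Where the code order happens to match the assumed effects (row 3 with PANC in the middle, row 4 with CRC in the middle), the difference is no larger than with no cancer effect at all. Elsewhere it is 0.048 to 0.099. The largest shift in the average estimate is from 1.216 to 1.149, or −0.067, in row 2 with CRC in the middle.

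For scale, the assumed response rates without a cancer effect are 1/(1 + e^1) = 0.269 on placebo and 1/(1 + e^−0.2) = 0.550 on 400 mg. The unadjusted standard error of the log odds ratio is √[1/(42 × 0.269 × 0.731) + 1/(42 × 0.550 × 0.450)] = √(0.1211 + 0.0962) ≈ 0.47. A mean shift of 0.10 is about a fifth of that.

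**The case against.** The strongest reply is that this is example code. It contains a comment saying that the step classifying deaths as non-response still has to be written, so it is a template. The methods text, which governs, includes the two terms only where appropriate and never calls cancer a score. The natural reading of that text is categorical. The only coding the appendix shows is text, and text would make the error obvious. The endpoint is not among those listed for formal testing in SAP 5.1, so it is exploratory.

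All of this stands, and it limits the consequence. It does not make the two statements right: no coding of one `cancer` variable makes them do what the ANCOVA block does.

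A reader might infer more than the documents support:

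- *That about 30% of Week 12 values are affected.* Protocol 9.5 gives roughly 30% as an assumed discontinuation rate. The share imputed is not stated. Censoring for prohibited treatments and for missed or incomplete doses could change it, and deaths are set to non-response whatever value is imputed.
- *That imputed values for the middle-coded cancer must lie between those of the other two.* Only the cancer term in the conditional mean is constrained. Each draw also depends on baseline, treatment, therapy, the other visits and random error.
- *That leaving out therapy distorts the odds ratios.* Step 4 shows that it does not.
- *That the code contradicts SAP 5.2.8 and 5.3.1.* Neither section states a parameterisation, and both leave inclusion to judgement.
- *That the primary result is at risk.* The MMRM and Emax analysis does not run through these blocks. The MMRM and Cox code could not be read in the text available here, so nothing is claimed about them.

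**Conclusion.** Wrong as written, and minor. Run as printed, the PROC MI and PROC GENMOD examples either stop (cancer as text) or silently replace a 2-degree-of-freedom factor with a 1-degree-of-freedom slope whose meaning depends on code order (cancer as numbers). The silent case requires numeric coding, which the documents neither specify nor exclude.

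The expected effect on the treatment odds ratios is small. Under the assumed cancer effects it averaged 0.03 to 0.10 on the log scale, a factor of at most e^0.099 ≈ 1.10. The 0.60 is the most extreme of the simulated runs and should not be read as typical. The simulation left out the imputation step, so it shows direction and rough size only. The reason to correct the code is that a reported odds ratio and p-value should not depend on an arbitrary coding choice.

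**What to change.** In PROC MI, use the ANCOVA block's own statement, "class treatment therapy cancer". In PROC GENMOD, use `class resp treatment therapy cancer;`. That adds two words to each of two statements and changes nothing in the design, the data collected or the primary analysis. Cancer type then takes 2 degrees of freedom in both models, the results no longer depend on how it is coded, and the per-arm LS-means odds are averaged over covariate levels in the same way as the ANCOVA LS means. If the production programs already declare both variables, only the appendix needs correcting.

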Appendix 5. Bayesian Emax Model Methodology Details

Data Provided by Programmer

A .csv dataset of LS means from the MMRM analysis should be produced by programming for use in R by the reporting statistician and QC statistician. The file should be in the following format (Note that column headers should be labelled as specified below (including capitalization), as R is case sensitive): -

Dose	Mean	SE
0	0	0.3
2.5	0.2	0.4
10	0.4	0.5
40	0.3	0.3
80	1.6	0.4
120	1.8	0.5

The residual standard deviation (Residual_SD) on Week 12 from the unstructured covariance matrix from the MMRM will also be provided by programming in a separate .csv file.

Fitting the Emax Model

The 4-parameter Emax model will be fitted using the latest version (currently 2.3.5) of the clinDR package. This analysis will be conducted by the reporting statistician. A different statistician will conduct QC of the analysis. The outputs of the analysis will be provided as .csv files to the programming team for creation of programming tables and figures.

The default burn-in and number of samples will be utilized along with thinning of 20, which will include 3 chains to assess convergence.

Model diagnostics will be examined, including trace and auto-correlations plots. If these raise concerns over model convergence, additional burn-ins, samples and thinning will be investigated to improve convergence. Changes to the priors below may also be considered (e.g. increase precision of hill) to improve convergence, if deemed necessary, and would be documented in final tables as appropriate. The final diagnostic plots will not be included in the clinical study report.

Priors Priors

Prior distributions will be specified for the placebo response (E_0), the difference in response (difTarget) between the highest dose (dTarget = 400mg) and placebo, and the residual standard deviation (sigma). Note that Emax is derived from other parameters and is thus not explicitly supplied.

Parameter	Prior
E ₀	t(Mean = -0.58, SD = 1.84, df=3)
difTarget	t(Mean = 0, SD = 49, df=5)
sigma	Uniform(lb=0.49, ub=49)

*E*₀: An informative meta-analytic predictive prior, based on historical results from internal and external studies, robustified by the inclusion of a weakly informative component to handle any possible prior-data conflict, will be used for the placebo change from baseline at Week 12. This will be approximated by a t-distribution with a mean of -0.58 kg, an SD of 1.84 kg and 3 degrees of freedom. If additional relevant data become available during the study, a sensitivity analysis may be performed by incorporating the new data, using the same approach as above.

difTarget: A vague t-distribution will be used for the 400 mg placebocorrected change from baseline at Week 12 with a mean of 0, a SD equal to 10 times the predicted standard deviation (ie, 49 kg) and 5 degrees of freedom.

sigma: A uniform prior will be used, with a range we are confident will include the population value. A lower bound of 0.49 kg and an upper bound of 49 kg will be used.

ClinDR default settings will be used to specify prior distributions for the Hill parameter and the ED₅₀. The default distributions in the current version of clinDR (version 2.3.5) are based on a meta-analysis of clinical dose response data and are listed below. These default distributions will be updated if the meta-data, and their analysis, are updated before the completion of the current study.

Parameter	Prior
log(ED ₅₀)	log(P ₅₀) + t(Mean=0, SD=1.73, df=5)
log(Hill)	t(Mean = 0, SD =0.85, df=5)

The correlation between these two parameters is currently -0.45 based on the analysis of the meta-data, which also would be updated if the historical analysis is updated.

The predicted ED₅₀ for the compound (P_{50}) is currently ~150 mg Q4W dose, based on latest data for the compound (this may be updated as new data become available).

R Code

The following R code is included as an example that will be used as a basis for the analysis:

library(clinDR) mmrmRes <- read.csv("LSmeans.csv", header=T, stringsAsFactors=F)

Determine 'effective' subject numbers based on MMRM SD at Week 12: mmrm_sd <- 0.825 # Provided by programming mmrmRes\$n <- trunc((mmrm sd/mmrmRes\$se)^2,0)

```

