## 9.5. Sample Size Determination

A sufficient number of participants will be screened to achieve a total of approximately 168 participants, with 42 participants randomly assigned to ponsegromab 100, 200 or 400 mg and placebo in approximately a 1:1:1:1 ratio. This is expected to ensure completion through Week 12 of the study of approximately 120 completing participants (30 in each of ponsegromab 100, 200 or 400 mg and placebo), assuming a discontinuation rate of approximately 30% (if this rate is higher, or there is a high rate of non-compliance, more participants may be randomized to ensure the required number of completing participants).

The sample size in the ponsegromab and placebo arms is based on the primary efficacy endpoint, mean change from baseline in body weight at Week 12. An informative meta-analytic predictive prior, based on historical results from internal and external studies, robustified by the inclusion of a weakly informative component to handle any possible prior-data conflict, will be used for the placebo response and is expected to equate to an effective sample size of 39 placebo participants. Further details on the prior derivation will be given in the statistical analysis plan SAP.

120 completing participants, in a 1:1:1:1 ratio, plus 39 participants from the placebo prior, gives acceptable Operating Characteristics in that:

- The probability of achieving statistical significance (at the 5% significance level, using a 1-sided t-test), for a true difference between ponsegromab and placebo of 2.7 kg, is approximately 80%.
- An observed difference between ponsegromab and placebo of 1.8 kg is expected to achieve statistical significance (at the 5% significance level, using a 1-sided t-test).

A conservative estimate of the standard deviation, for the change from baseline in body weight at 12 weeks of 4.9 has been used.

The sample size determination has been performed using pairwise comparisons. This is considered to be a conservative approach since the primary analysis will utilize a Bayesian  $E_{max}$  dose-response model, which would be anticipated to best describe the dose-response in the presence of an effective compound.

Evaluable participants are defined as in Section 9.2. Participants who withdraw from the study will not be replaced.

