5. GENERAL METHODOLOGY AND CONVENTIONS

5.1. Hypotheses and Decision Rules

The null hypothesis of no difference between ponsegromab and placebo will be tested for each primary, and selected secondary (physical activity, FAACT and CRCSD) and tertiary (PROMIS-fatigue, PROMIS-physical function, LSMI and survival status) endpoints. The alternative hypothesis is that ponsegromab is superior to placebo. The Type I error rate (α-level) used for the statistical inference will be 5% (1-sided). Each dose of ponsegromab will be compared separately with placebo. No adjustment for multiple comparisons will be made.

For all other endpoints, the results of any statistical analyses are for exploratory purposes only and there is no formal hypothesis testing.

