6.1.1.1. Main Analysis

Absolute values, changes from baseline and percent changes from baseline in body weight will be summarized descriptively by treatment group and timepoint, as described in Section 5.2.1. Tables will include baseline and all post-baseline timepoints. Box and whisker plots (or similar) of absolute values, changes from baseline and percent changes from baseline over time will also be produced, with all treatments on the same plot.

Change from baseline in body weight will be analyzed using an MMRM model as described in Section 5.2.3. All post-treatment dosing timepoints up to Week 12 (ie. Weeks 4, 8 and 12) will be included in the model. Additional terms for type of therapy [i.e. platinum or not] and type of cancer will be fitted in the model. Additional plots of LS means and differences (including 90% CIs for both), for Week 12 only, will be produced over treatment.

A Bayesian E_{max} model, as described in Section 5.2.4, will then be fitted to the Week 12 LSmeans and SEs from the MMRM analysis. This will be used to estimate the treatment effect related to the primary Estimand 1 (as described in Section 2.2.1). If the E_{max} model analysis is not performed, the primary results for the study will be based on the MMRM results at Week 12.

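### The Emax step ignores the covariance of the adjusted LS means and rounds effective n down, so the primary credible intervals can be slightly misstated, usually too wide

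*SAP*

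**What the plan says.** SAP 6.1.1.1 fits an MMRM to the change in body weight at Weeks 4, 8 and 12, with added terms for therapy (platinum or not) and cancer type. The Emax model "will then be fitted to the Week 12 LSmeans and SEs from the MMRM analysis", and its output is the primary estimate.

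SAP Appendix 5 defines the hand-over: a file with dose, mean and SE, and a separate file with the Week 12 residual SD. Under the comment "Determine 'effective' subject numbers based on MMRM SD at Week 12", the example R code computes (SD/SE)², truncates it to an integer and passes these values as per-dose counts with a single variance. No covariance between the LS means is exported or used. The SAP describes this code as an example on which the analysis will be based.

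The margins of the MMRM LS means are not visible. SAP Appendix 4 has a heading for the MMRM code, but the text available for this review shows no code under it. The ANCOVA example has "lsmeans treatment / diff cl alpha=0.1" and no observed-margins option.

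**The concern.** A covariate-adjusted LS mean contains sampling error from the estimated covariate effects. If all arms are evaluated at the same covariate values, and those values lie away from the enrolled averages, that error is common to the arms and cancels in a difference. A model that sees only four separate SEs cannot cancel it and counts it once in each arm. Truncation then removes up to one further effective participant per arm.

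At stake is the width of the 90% credible intervals for the dose-placebo differences, which are the primary result. As the SAP stands, that width depends partly on a software setting that is not visible and on the case mix that happens to be enrolled.

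**Working it through.** **Inputs from the documents.** SD: "A conservative estimate of the standard deviation, for the change from baseline in body weight at 12 weeks of 4.9 has been used" (Protocol 9.5). Design: 30 completers per arm plus 39 placebo-equivalents from the prior, one-sided 5%. Cancer mix 4:4:3 (Protocol 4.3). Priors from SAP Appendix 5.

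**Assumptions, not in the documents.** Platinum share 10% to 50%; SDs of 2.8 and 4.0 kg at Weeks 4 and 8; between-visit correlations 0.65 to 0.8; the dropout pattern; illustrative LS means for the Emax check.

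**1. The plan's own figure.** SE = 4.9 × √(1/30 + 1/69) = 1.07 kg. Power = Φ(2.7/1.07 − 1.645) = 80.9%, or 80.4% with the noncentral t. The protocol's statement "for a true difference between ponsegromab and placebo of 2.7 kg, is approximately 80" per cent is therefore reproduced. The critical difference is 1.76 to 1.78 kg, against the stated 1.8 kg. This pairwise calculation uses neither LS means nor effective counts, so neither feature enters it.

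**2. Truncation alone.** The worst case is an effective n just below 31, cut to 30: √(31/30) = 1.0165. At n = 20 it is √(21/20) = 1.025. The factor is never below 1.

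**3. Independence alone.** The ratio of the SE used to the correct SE of a difference is √(SE₀² + SE_d²) / √(SE₀² + SE_d² − 2cov). With equal SEs and LS-mean correlation ρ this is 1/√(1 − ρ): above 1 for positive ρ, below 1 for negative ρ.

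**4. Size under the planned MMRM.** SAP 5.2.3 gives by-time interactions to baseline and treatment only, so the therapy and cancer effects are estimated from all three visits. A generalised least squares version of that model, with equal-weight margins and the 4:4:3 mix, was run both with 30 per arm and with 168 randomised and 30% dropout. It gives these mean ratios (ranges are across runs):

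| Platinum share | Independence alone | Plus truncation |
|---|---|---|
| 50% | 1.000 | 1.007–1.011 |
| 30% | 1.006–1.008 | 1.014–1.015 |
| 20% | 1.017–1.022 | 1.027–1.031 |
| 15% | 1.031–1.038 | 1.04–1.049 |
| 10% | 1.061–1.071 | 1.070–1.083 |

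Sensitivity:
- A cancer mix of 75/15/10% gives 1.048 at 50% platinum and 1.065 at 20% (largest single replicate 1.14), both with truncation. At 20% the mean correlation is 0.10, and 1/√(1 − 0.10) = 1.054 agrees with the simulated 1.056 before truncation.
- Equal SDs at all visits, an unfavourable choice, give 1.048 at 20% platinum and 1.081 at 15% before truncation.
- Observed margins give a mean of 0.999 for independence alone, below 1 in 62–68% of comparisons and by up to 2–3% in single ones. With truncation the mean is 1.006–1.007.

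**5. Through the Emax model.** With the SAP priors and sigma fixed at 4.9, the posterior SD of the 400 mg difference, relative to an analysis with the full covariance, is:

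| ρ | Independence alone | Plus truncation |
|---|---|---|
| −0.02 | 0.992 | 1.004 |
| 0.02 | 1.008 | 1.015 |
| 0.05 | 1.021 | 1.028 |
| 0.10 | 1.043 | 1.050 |
| 0.20 | 1.093 | 1.101 |

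At ρ = 0.05 and effective n 30.5, the 90% interval moves from 0.65–4.19 kg to 0.59–4.23 kg. Its width goes from 3.54 to 3.64 kg.

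**The case against.** The strongest reply is that the premise for most of the effect cannot be seen. The MMRM code is not shown, and the ANCOVA example belongs to a different endpoint. If the MMRM uses observed margins, the net error is under 1%. The R code is only an example. The usual direction is conservative, and the MMRM differences, whose CIs and p-values come directly from the model, are reported as well. All of this stands and limits the size. It does not remove the two mechanisms, which are in the hand-over as written. The MMRM result becomes primary only if the Emax analysis is not performed.

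Three stronger readings are tempting and not supported.

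- A reader might infer that the SEs are always overstated. Truncation always widens, but the sign of the independence error follows the sign of the covariance.
- A reader might size the effect from a Week 12-only model. With N = 120, n = 30 per arm and platinum share p, that gives √(1 + n(0.5 − p)²/(N·p(1 − p))) = 1.068 at 20% and 1.114 at 15%. The planned model uses three visits, and under the growing visit SDs assumed here the figures are about 1.02 and 1.03–1.04.
- A reader might turn the inflation into a loss of the stated power. The protocol's SE of 1.07 kg comes from a pairwise t-test with prior participants added, and neither feature enters it.

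A reader might also infer that equal-weight margins move the placebo mean away from what the historical prior describes. The documents do not give the historical platinum or cancer mix, so this cannot be judged.

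**Conclusion.** The point holds in conditional form. The primary Emax step discards the LS-mean covariance and rounds effective n down. With equal-weight margins and the 4:4:3 cancer mix, the SE of a dose difference is overstated by about 1% to 8% on average as the platinum share goes from 50% to 10%. With observed margins the net overstatement is under 1%. An uneven cancer mix, or visit SDs that do not grow over time, would raise the equal-margin figures at a given platinum share.

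These sizes rest on assumed visit SDs, correlations and platinum shares, and on margins that are not visible. The error is usually conservative. It gives no sign of an inflated type I error and does not touch the stated sample size or power. It is a small defect, worth correcting because it sits in the primary analysis and is avoidable.

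**What to change.** Export the 4×4 covariance matrix of the Week 12 LS means from the MMRM and use it in the Emax likelihood in place of independent counts. If sigma is to keep its uniform prior, supply the matrix divided by the squared residual SD and let sigma² scale it. If effective counts are kept instead, use the unrounded (SD/SE)² and say in the SAP that the covariance is ignored.

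State the LS-mean margins as well. Observed margins are a choice of target case mix and are not needed for this correction once the covariance is passed.

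Cost: one extra output from the MMRM program, a changed likelihood input in the R program, and its quality check. The call shown takes only counts and one variance. If the fitting function cannot accept a matrix, a short multivariate-normal likelihood has to be written and verified. No data collection or design change is involved.
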